1.3 SCHEDULE OF ACTIVITIES (SOA)

Study Week ^k	-1	0	2 ^d	4 ^d	6 ^d	8 ^d	10 ^d	12 ^d	14 ^{e,f} (end of study safety visit)
Informed Consent	X ^b	X ^b							
Inclusion/exclusion	X ^b	X ^b							
Pregnancy Test	X ^b	X ^b		X		X		X	
HIV, HBV, HCV testing	X ^{b,j}	X ^{b,j}							
Medical History	X ^b	X ^b							
Medical assessment ^a	X	X	X	X	X	X	X	X	X
Physical Exam	X ^b	X ^b							
Follow up and labs ^{c,d} : CBC, BMP, LFTs, LDH, absolute reticulocyte count, haptoglobin, stool occult blood, urinalysis	X ^b	X ^b	X	X	X	X	X	X	X
Study drug (fostamatinib) administration ^g		X	X	X	X	X	X		
B-cell chimerism and Cytokines ^h		X ^b		X		X		X	
IBLS [1] ⁱ	X ^b	X ^b	X	X	X	X	X	X	
cPRA, MFI, immunoglobulin level, RBC antibody		X		X		X		X	

- a) Vital signs, transfusion support evaluation, concomitant medication review and steroids taper assessment
- b) Can be done within 7 days before or at time of enrollment
- c) Follow up visits will be completed as outpatient in-person visits at the NIH Clinical Center, or via telehealth/telephone if patients are unable to travel for any reason (except for weeks 4 and 12 where patients are required to return to the NIH Clinical Center). Labs can be completed locally, and results will be provided to the research team.
- d) Can be performed +/- 4 days from scheduled visit.
- e) Outpatient visit can be +/- 3 days from scheduled visit.
- f) Patients who rolled over to 000760-H will not need to return for week 14 visit, they will transition all study follow up to 000760-H. The patients who do not roll over will complete their week 14 safety visit on 000758-H.

Abbreviated Title: Fostamatinib for post-transplant cytopenias

Version Date: 11/28/2023

- g) Study drug will be mailed from Rigel or the clinical center pharmacy and be distributed to the research subjects from the pharmacy directly to the research subjects. The pill count will be reviewed every 2 weeks at the medical assessment visit.
- h) Including CRP, IL-1, IL-2, IL-6, IFN γ , TNF α , EPO and TPO
- i) See Appendix B
- j) Within 6 months

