- Subjects on other standard of care therapeutic regimens for GVHD or cytopenias should be on a stable dose of medication (no change $\geq 25\%$) for at least 15 days prior to enrollment.
- Patients with a history of hypertension should be maintained on a stable antihypertensive regimen and with controlled blood pressure (Systolic blood pressure < 140 mmHg and diastolic blood pressure < 90 mmHg) for at least one week prior to enrollment.
- Peripheral blood or bone marrow T-cell chimerism $\geq 50\%$ donor cells
- [‡] Immune mediated anemia in subjects with auto or alloantibodies identified due to ABO or non-ABO mismatch transplant, or thrombocytopenia due to identified HLA/HPA antibody. Other causes of immune mediated cytopenias include clinically diagnosed (with or without serologic confirmation) idiopathic thrombocytopenic purpura or autoimmune hemolytic anemia. Subjects with cytopenias attributable to GVHD will be included. Subjects with idiopathic immune mediated cytopenias can also be included. Subjects with evidence for graft rejection per the investigator's opinion ARE NOT eligible for treatment.

* Steroid dependence is defined as inability to tolerate a corticosteroid taper after demonstrating a response to an initial corticosteroid dose (typically 1-2 mg/kg/day). Patients will meet our definition of steroid dependence if their cytopenias relapse or progress before achieving a 50% decrease in the initial corticosteroid dose and/or are unable to have their steroid dose tapered to a dose of less than 20 mg/day of prednisone.

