- In the event that the subject is unable to tolerate 100 mg BID, the dose can be reduced to 150mg daily with re-assessment. If intolerable AEs with 150 mg daily, dose can be reduced to 100 mg daily. If unable to tolerate 100mg daily, patient will stop fostamatinib and will be off study. Intolerance is considered as any grade 3-4 AEs, probably or definitely related to fostamatinib, or any grade AE which, at the PI's discretion, appears to be distressing enough to the patient to lead to the drug's discontinuation. If the adverse events resolved and subject tolerates the dose reduction with no recurrence of AE, per PI discretion subject can be re-escalated one level at a time until back to the maximum tolerable dose.
- Causes of neutropenia in a AHCT recipient may include: infections such as cytomegalovirus infection, medication such as ganciclovir or other antibiotics, immunosuppressants such as mycophenolate or ruxolitinib, graft failure, relapse of primary disease. If neutropenia occurs, we will perform an extensively work up on the patient for the other causes stated above, and/or hold other potential culprit medications. We will give filgrastim to patients while doing the above work up. If no other causes are found, and the neutropenia does not recover, or recurs, with holding other medications, we will conclude that fostamatinib is contributing to the development of neutropenia.
- GvHD may mimic adverse events. If holding fostamatinib according to the DSR does not reverse the diarrhea, abdominal pain, transaminase elevation, AND there are no other causes (such as infection) identified, we will consider the cause of the adverse events to possibly be related to GVHD. In such circumstances, we will make every effort possible to perform biopsies of the involved organ systems to confirm the diagnosis of GvHD.

Dose adjustment for platelet counts and hemoglobin are as the following:

Thrombocytosis	
PLT $\geq 200 \times 10^9 /L$ to $\leq 400 \times 10^9 /L$ at any time	
 • Decrease the dose to the next lower dose level. Wait 2 weeks to assess the effects of this and any subsequent dose adjustments.
PLT $> 400 \times 10^9 /L$ at any time	
 • Stop fostamatinib. Increase the frequency of platelet monitoring to twice weekly. • Once the platelet count is $< 150 \times 10^9 /L$, resume fostamatinib at the next lower dose level

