7.2 PARTICIPANT DISCONTINUATION/WITHDRAWAL FROM THE STUDY

Prior to removal from study, effort must be made to have all subjects complete a safety visit approximately 14 days following the last dose of study therapy.

- Participants are free to withdraw from participation in the study at any time upon request.
- Participants can be taken off study at any time per site principle investigator discretion (e.g. for significant noncompliance or if the PI believes it would be in the subject's best interest).
- Patients rolled over to Extended Access protocol 000760 will be discontinued from this protocol.

The reason for participant discontinuation or withdrawal from the study will be recorded on the Case Report Form (CRF). Subjects who sign the informed consent form but do not receive the study intervention may be replaced.

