8.2.2 Biospecimen Evaluations

Research bloods will be sent to the NIH for processing in either the clinical laboratory or in a NHLBI research lab.

The amount of blood that may be drawn from adult patients (i.e., those persons 18 years of age or older) for research purposes shall not exceed 300 mL over any eight-week period.

Please refer to laboratory manual for further information about processing and shipment.

Table of samples to be collected*				
Test/assay	Volume blood (approx.)	Type of tube	Frequency	Location of specimen analysis
Routine* 
 • CBC • Absolute reticulocyte count • BMP • Hepatic pane • Lactate dehydrogenase • haptoglobin 	3 mL 4 mL	EDTA tube Lithium Heparin tube (light green)	Baseline (prior to treatment) and then biweekly on follow up visits	NIH clinical lab or Clinical Lab At participating sites
Research* 
 • STR Chimerism, CD19 	6 ml	EDTA tube	Baseline, then W4,8,12	NHLBI Research Lab ([name]), NIH Clinical Lab (Molecular Hematology, 2C324)
Research* 
 • Type and screen 	6 mL	EDTA tube	Baseline, then W4, 8, 12	NIH Clinical Lab or, Clinical Lab At participating sites**

Abbreviated Title: Fostamatinib for post-transplant cytopenias

Version Date: 11/28/2023

Table of samples to be collected*				
Test/assay	Volume blood (approx.)	Type of tube	Frequency	Location of specimen analysis
Research* • Immunoglobulins, quantitative (IgA, IgG, IgM)	3.5 mL	Lithium Heparin tube (light green)	Baseline, then W4, 8, 12	NIH Clinical Lab Or, Clinical Lab At participating sites***
Research* • HLA antibodies (Class 1 A, B, C and Class 2 DRB1, DQB1) • MFI	10 mL	EDTA tube	Baseline, then W4, 8, 12	NIH Clinical Lab
Research* • CRP	4 mL	Lithium Heparin tube (light green)	Baseline, then W4, 8, 12	NIH Clinical Lab or Clinical Lab At participating sites
Research* • Erythropoietin	3.5 mL	Red top tube (SST3.5)	Baseline, then W4, 8, 12	NIH Clinical Lab
Research* • IL-6	6 mL	EDTA (lavender)	Baseline, then W4, 8, 12	NHLBI Research Lab ([name])
Research* • Expanded cytokine panel • Thrombopoietin	16 mL	Red top tube (serum)	Baseline, then W4, 8, 12	NHLBI Research Lab ([name])
Research* • Lymphocyte subsets • PBMC	20 mL	Sodium Heparin (green top)	Baseline, then W4, 8, 12	NHLBI Research Lab ([name])

* Residual bloods from clinical care can be transferred to the NHLBI research lab for storage

Abbreviated Title: Fostamatinib for post-transplant cytopenias

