In this study, we would not enroll patients with evidence of graft failure (sections 5.2). Therefore, in this study any graft failure that occurs would be secondary graft failure, which is a known complication of allogeneic stem cell transplantation. Secondary graft failure rates vary in incidence according to the type of transplant, but in general would not be expected to occur in more than 10% of patients [25, 26]. Secondary graft failure is defined as initial blood or marrow donor myeloid chimerism $\geq 5\%$ declining to $< 5\%$ on subsequent measurements. If chimerism assays are technically not possible in the setting of declining blood count in a subject with prior neutrophil recovery and the absolute neutrophil count is sustained at $< 500/\text{mm}^3$, in the absence of other causes, this will be counted as secondary graft failure.

We wish to assure that the rate of secondary graft failure of this study is no more than 10%. We will use a Bayesian approach by Geller et al. [24]. The stopping boundary is reached if the Bayesian posterior probability that the true probability of secondary graft failure exceeds 0.10 is at least 90%. We take our

Abbreviated Title: Fostamatinib for post-transplant cytopenias

Version Date: 11/28/2023

prior distribution to be a beta distribution so that our prior clinical opinion is worth 20% of the weight we will place on the new data. This gives prior parameters alpha = 0.4, beta = 3.6. The following table summarizes the threshold numbers for the boundary, which would lead to a recommendation to stop the study due to excess graft failure.

Number of subjects in the study	Stop if the number of subjects who have developed graft failure
2 - 4	2
5 - 11	3
12 - 17	4
18 - 20	5

We investigated the performance of the above stopping rule by a simulation study. In each simulation run, we generated a study with 20 independent Bernoulli trials; each had a probability p for having graft failure, and compared the graft failure outcomes with the above stopping boundary to determine whether the study was stopped. We repeated the simulation 100,000 times and computed the proportion of stopped studies using the above stopping rule. The following table summarizes the performance of the stopping rule under a number of scenarios for secondary graft failure probability p :

Probability of secondary graft failure = p	0.05	0.10	0.15	0.2	0.25	0.3
Proportion of Stopped Studies	3%	14%	34%	55%	73%	86%

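### The graft-failure stopping rule depends mainly on donor myeloid chimerism, which the protocol never schedules, and it has no time window

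*Combined protocol and SAP*

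**What the plan says.** **Event.** Section 9.3.4 C begins: "Secondary graft failure is defined as initial blood or marrow donor myeloid chimerism" of at least 5% which falls below 5% on later measurements. It adds a second route: "If chimerism assays are technically not possible in the setting of declining blood count", in a subject whose neutrophils had recovered, a neutrophil count sustained below 500/mm³ is used, and "in the absence of other causes, this will be counted as secondary graft failure".

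**Assays.** The chimerism row of the Schedule of Activities (section 1.3) reads "B-cell chimerism and Cytokines", at weeks 0, 4, 8 and 12. The sample table in section 8.2.2 lists "STR Chimerism, CD19" at baseline and weeks 4, 8 and 12. Section 5.1 requires "Peripheral blood or bone marrow T-cell chimerism" of at least 50% donor cells. Donor myeloid chimerism appears only in section 9.3.4 C.

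**Neutropenia.** Section 6.1.2.3 lists graft failure among the causes of neutropenia to be worked up. If no other cause is found and the neutropenia does not recover or recurs, "we will conclude that fostamatinib is contributing to the development of neutropenia".

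**Window.** The rule for treatment-related serious adverse events (TRSAE) in section 9.3.4 B is tied to 12 weeks. The graft-failure rule gives no period. Section 7.2 says: "Patients rolled over to Extended Access protocol 000760 will be discontinued from this protocol". Under section 1.3 these subjects skip week 14, and the others attend it.

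**Numbers.** Both safety tables and both simulations end at 20 subjects. Section 9.1 allows up to 8 more to make up for early discontinuations and assesses safety in everyone with at least one dose. The synopsis gives 20 in total.

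**The concern.** A stopping rule is only as good as the event it counts. If the plan is followed as written, the DSMB receives no scheduled measurement for the main graft-failure criterion. A CD19 result describes B cells and cannot settle whether donor myeloid chimerism has fallen below 5%.

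The fallback does not close the gap. The CBCs every two weeks would show a low neutrophil count, but the text admits that route only when the assay cannot technically be done. A myeloid decline with preserved counts would be seen only if someone happened to order the test.

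With no window, it is also unclear for how long each subject is at risk in the rule. Follow-up under this protocol differs between subjects who roll over and those who do not.

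The stated performance describes a trial in which every failure is observed. Under-ascertainment can only lower the probability of stopping, and the printed table would not show it.

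**Working it through.** **1. Set the assays against the event.**

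| Place | Lineage | Timing |
|---|---|---|
| 9.3.4 C, event definition | Myeloid | Initial and later, times not given |
| 1.3, schedule | B cell | Weeks 0, 4, 8, 12 |
| 8.2.2, sample table | CD19 | Baseline, weeks 4, 8, 12 |
| 5.1, entry | T cell | Entry |

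No row supplies the lineage that the definition needs. An initial myeloid value might be found in existing records, which section 8.1.1 allows staff to review. No later value is scheduled.

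**2. Reproduce the plan's boundary.** The inputs from 9.3.4 C are a Beta(0.4, 3.6) prior, a limit of 0.10 and a posterior cut of 0.90. After s failures in n subjects the posterior is Beta(0.4 + s, 3.6 + n − s). The boundary is the smallest s for which P(p > 0.10) is at least 0.90. At n = 20, s = 4 gives 0.866 and s = 5 gives 0.953, so the threshold is 5, as printed. Every printed graft-failure threshold reproduces. So does every TRSAE threshold, from Beta(1, 3) and a limit of 0.25.

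**3. Reproduce the plan's performance.** I used an exact sequential binomial recursion, checking the boundary after each of 20 subjects.

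| True graft-failure rate | 0.05 | 0.10 | 0.15 | 0.20 | 0.25 | 0.30 |
|---|---|---|---|---|---|---|
| Printed stopping | 3% | 14% | 34% | 55% | 73% | 86% |
| Exact | 2.8% | 14.4% | 33.7% | 54.9% | 73.0% | 85.8% |

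**4. Effect of incomplete detection.** Suppose each failure is detected independently with probability d and missed failures count as non-events. The rule then sees a rate of p × d, and the plan's own table gives the answer. For a true rate of 0.20:

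- d = 0.75: 0.20 × 0.75 = 0.15, stopping about 34%.
- d = 0.50: 0.20 × 0.50 = 0.10, stopping about 14%.
- d = 0.25: 0.20 × 0.25 = 0.05, stopping about 3%.

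With full detection it is 55%. The documents give no detection rate, so the values of d are illustrative.

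**5. Beyond 20 subjects.** The maximum dosed is 20 + 8 = 28. The same priors and cut give these thresholds:

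- TRSAE: 9 at 21–23, 10 at 24–26, 11 at 27–28. For example, 8 of 21 gives a posterior of 0.879 and 9 of 21 gives 0.945.
- Graft failure: 5 through n = 25 (5 of 25 gives 0.901), then 6 at 26–28 (5 of 26 gives 0.888).

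If all 28 are at full risk, stopping at a true 25% TRSAE rate is 21.0%, against 18.3% for 20 subjects (printed 19%). At 10% graft failure it is 17.6% against 14.4%. Each prior is worth 4 subjects, which is 4/20 = 20% of the planned data but 4/28 = 14% of 28.

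**The case against.** The best defence is that relevant data may still reach the DSMB. Section 10.8.1 brings clinical laboratory data into the database, so a chimerism test ordered in routine care could be captured. Section 6.1.2.3 promises an extensive work-up of neutropenia, with graft failure among the causes to be examined. Both points stand. A reader might infer that the DSMB would have no graft-failure information at all, and the documents do not support that. Neither source is uniform, however, and neither covers a myeloid fall with preserved counts.

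A reader might also infer that sections 6.1.2.3 and 9.3.4 C flatly contradict each other on unexplained neutropenia. They do not, because section 6.1.2.3 considers graft failure before attributing the neutropenia to the drug. Some overlap remains: each passage assigns the residual unexplained case to its own category.

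On numbers, a reader might conclude that the tables fail once more than 20 subjects are dosed. Two extreme calculations seem to show this, and neither is evidence of harm:

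- Holding the TRSAE threshold at 8 through n = 28 gives 42.5% stopping at a true 25% rate, but it breaches the written 90% posterior criterion, which applies at any n.
- Adding 8 discontinuers with no risk of an event cuts stopping at 40% TRSAE from 67% to 32%, and at 20% graft failure from 55% to 39%. Nothing in the documents makes their risk zero. Section 9.3.4 C calls graft failure a known complication of transplantation, and section 7.1 keeps subjects who stop the drug in follow-up. At half risk, 8 extra subjects give about 54% for graft failure, close to the planned 55%.

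Section 9.3.4 B also refers to subjects evaluable for TRSAE by 12 weeks, so 20 evaluable subjects is the natural reading. What remains is a clarification.

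**Conclusion.** The point holds for the event definition. The main criterion of a safety stopping rule has no scheduled measurement, the fallback does not cover an assay that was simply not ordered, and the rule has no time window. That the assay is missing follows from the text alone. The size of the loss depends on how often failures would be found by other means, which the documents do not say. At a true 20% rate, stopping runs from 55% with full detection down to 34%, 14% or 3% at 75%, 50% or 25% detection, with missed failures counted as non-events.

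The boundaries are not wrong. Every printed threshold reproduces, and the graft-failure stopping probabilities agree with the exact values to rounding. Crossing a boundary produces a recommendation to stop, not an automatic halt. The unstated denominator is secondary: at full risk, going from 20 to 28 subjects moves stopping at the limiting rates by about 3 points (18.3% to 21.0% for TRSAE, 14.4% to 17.6% for graft failure).

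**What to change.** **Main change: reconcile section 9.3.4 C with sections 1.3 and 8.2.2.** Either option would do.

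- Add a myeloid fraction to the chimerism draws already planned at baseline and weeks 4, 8 and 12. This needs no new visit. The laboratory cost is small, and the laboratory must confirm that the sample is sufficient.
- Restate the event from data already collected, so that the neutrophil-count route does not depend on the assay being technically impossible. This adds no assay, but the text must say that chimerism falls with preserved counts are then missed.

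**With either option:**

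- State a common window. Twelve weeks would match the TRSAE rule and is the last point shared by subjects who roll over and those who do not.
- Reconcile the other-causes wording in section 9.3.4 C with the attribution of neutropenia in section 6.1.2.3, so that one case is not open to two classifications.

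**Secondary clarification.** State which subjects index the two safety tables, and reconcile the synopsis total of 20 with the up to 28 that section 9.1 permits. If all dosed subjects count, print the extended thresholds from step 5, note that the priors are then worth 14% of 28 subjects, and restate the performance. If the 20% weight is kept instead, the priors become Beta(1.4, 4.2) and Beta(0.56, 5.04), and a few thresholds rise by one: TRSAE at n = 20 to 9, and graft failure at n = 11 to 4 and at n = 25 to 6. Leaving dosed subjects out of the count would first have to be squared with the at-least-one-dose safety population in section 9.1. The cost is a short text change, plus a table extension and a simulation rerun if the count goes past 20.

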10 REGULATORY AND OPERATIONAL CONSIDERATIONS

10.1 INFORMED CONSENT PROCESS

10.1.1 Consent/Assent Procedures and Documentation

Non-NIH Enrolling Sites

Informed consent shall be documented using the current IRB-approved consent form. The investigational nature and objectives of this trial, the procedures and treatments involved, and their attendant risks and discomforts and potential benefits will be carefully explained in person to the patient, and a signed informed consent document will be obtained by the PI or any person authorized to consent.

When consent is obtained, the consent document(s) must be signed and dated by the subject, and the person obtaining consent. Telephone or any institution-approved electronic consent process can be used. The original, signed informed consent document will be placed in the medical record, and the subject will receive a signed copy of the informed consent document. Documentation of informed consent and the signed consent form will be maintained per institution requirements.

NIH Clinical Center

Informed consent will be conducted following OHSRP Policy 301- Informed Consent. An IRB-approved consent form will be provided to the participant or consent designee(s) (legally authorized [LAR] if participant is an adult unable to consent) electronically or by hard copy for review prior to consenting. The initial consent process as well as re-consent, when required, may take place in person or remotely (e.g., via telephone or other NIH approved platforms). The investigational nature and objectives of this trial, the procedures, and their attendant risks and discomforts and potential benefits will be carefully explained to the participant in a private setting. The participant will be given as much time as they need to review the document and to consult with their family, friends, and personal health care providers. In addition, a study team member will be available to answer any questions. A signed and dated informed consent document will be obtained by any investigator authorized to consent prior to entry onto the study. Consent may be obtained with required signatures on the hard copy of the consent or on the electronic document. When a document that is in electronic format is used for obtaining consent, this study may use the iMed platform which is 21 CFR, Part 11 compliant, to obtain the required signatures. During the consent process, participants and investigators may view the same approved consent document simultaneously when participant is being consented in person at the Clinical Center or both may view individual copies of the approved consent document on screens in their respective locations remotely. Signatures may be obtained either by both directly signing on the device that the consenting investigator is using (when in person) or through iMed Mobile Signature Capture (remotely) which allows texting or emailing a link to the participant. That link allows the participant to review the consent, then proceed to sign on the device they are using. Whether hard copy or electronic, both the investigator and the participant will sign the document with a hand signature using a pen (if using hard copy), finger, stylus, or mouse (if electronic). When done remotely, if the participant prefers to sign a hard copy, they may be instructed to sign and date the consent document during the discussion and mail, secure email or fax the signed document to the consenting investigator. Whether in person or remotely, the privacy of the participant will be maintained. Finally, the fully signed informed consent document will be stored in the electronic medical record, and the participant will receive a copy of the signed informed consent document.

Telephone consent: When appropriate, the consent will be sent to the subject to be executed by telephone. The investigational nature of the protocol will be carefully explained to the subject. An investigator with consenting rights will lead this discussion. The subject will be directed to sign and date the consent. The original informed consent document will then be sent back to the principal or associate investigator who led the discussion, who will sign and date the consent form with the date it was returned. A fully executed copy will be returned via mail for the subject's records. The informed consent process will be documented in the medical record. The investigator will confirm that, when required, written legally effective consent has been obtained prior to initiating any study interventions.

